### **3. Inclusion and Exclusion Criteria:**

Patients over the age of 18 with renal function compatible with dosing of dabigatran and meeting all indications for watchman LAA closure device implantation as an alternative to long-term anticoagulation (CMS coverage criteria, CHADS 2 Vasc 3-9, and seeking suitable rationale for a non-pharmacologic stroke protection option). Lab testing and imaging will be part of standard of care for follow-up after LAA closure implantation including BMP, INR (when on warfarin) and baseline rhythm on day of implant, 90-day and 1-year transesophageal echo and when indicated CT angiography (subjects unable to undergo TEE at follow up). Images will be interpreted by the TEE operator, and an either independent radiologist or echocardiographer at Vanderbilt University Medical Center, the coordinating center.

#### **Inclusion Criteria:**

1. Male or female sex, age >18 years.
2. CHADS2 Vascular score of 3-9 and HAS BLED score 2 or higher meeting CMS coverage criteria for Watchman LAA closure device implantation.
3. Able to give informed consent.
4. Life expectancy of > 1year in the judgment of the implanting physician and shared decision-making physician.

To be eligible for enrollment, patients must NOT meet any of the following criteria.

#### **Exclusion Criteria:**

1. Unable to give informed consent
2. History of confirmed allergy to dabigatran etexilate
3. Active cerebral bleeding, or active non-cerebral bleeding requiring blood transfusions (any absolute contra-indications to anti-coagulation).
4. History of intraocular, spinal, retroperitoneal or a traumatic intra-articular bleeding unless the causative factor has been permanently eliminated or repaired (e.g. by surgery)
5. Gastrointestinal (GI) haemorrhage within one month prior to screening, unless, in the opinion of the Investigator, the cause has been permanently eliminated (e.g. by surgery)
6. Major bleeding episode (reduction in the haemoglobin level of at least 2g/dL, transfusion of at least two units of blood, or symptomatic bleeding in a critical area

or organ) including life-threatening bleeding episode (symptomatic intracranial bleeding, bleeding with a decrease in the haemoglobin level of at least 5g/dL or bleeding requiring transfusion of at least 4 units of blood or inotropic agents or necessitating surgery) in one month prior to screening visit

7. Intolerance to dabigatran, if medication naïve, or other contra-indications as per the USPI, including ESRD on hemodialysis or GFR < 15ml/min, or concomitant use of rifampin.
8. History of non-compliance, inability to follow-up.
9. Pre-menopausal women (last menstruation ≤ 1 year prior to screening) who are not surgically sterile.
10. Ischemic stroke or hemorrhagic stroke within 90 days of LAA placement.
11. Anatomy unsuitable for LAA closure (incomplete surgical LAA ligation without suitable anatomy for Watchman placement. LAA ostial measurements >31mm, or <17mm in all views).
12. Requires long-term oral anticoagulation therapy for a condition other than atrial fibrillation.
13. ASA allergy, or confirmed allergy to nickel.
14. Prior PFO or ASD closure device or prosthetic or mechanical heart valve.
15. Acute MI within 90 days.
16. Platelets <50,000 at time of Watchman LAAC implantation.
17. Active endocarditis.
18. Planning for endocardial catheter AF or left atrial ablation within 90 days of Watchman implantation.

Dosing regimen of dabigatran will be by FDA and pharmacokinetic labeling for dabigatran 150mg BID dosing if Creatinine clearance >30mL/min, and 75mg BID dosing if 15-30mL/min. This will be based on calculated CC by baseline labs performed on day of implant. Additional dosing adjustments per package insert for patients taking dronedarone 400mg BID, or ketoconazole will be made consistent with drug label. The majority of subjects will be expected to be on 150 mg BID for 90 days. Subjects on 75 mg twice daily dosing may be enrolled if renal function is stable in the range of 15-30mL/min. Aspirin 81 mg a day will be taken along with oral anticoagulation for 90 days followed by longer-term aspirin 81 mg daily aspirin dose. At the 90 days TEE follow up (3 months) a PCV or CBC will be drawn and compared to baseline PCV pre-LAA closure implant as an assessment of

indolent blood loss (there is expected intra-procedural blood loss from back bleed on access sheaths estimated 25-125mL).

Drug required for study: Initially start with 100 subject pilot study on therapy for 90 days, with option to expand to full non-inferiority study if collaborative funding is secured (IF study expands beyond pilot, estimate 262 subjects, 90 days on therapy). Estimate 80% or more subjects on 150mg BID dosing, and up to 20% subjects on 75mg BID dosing. With either the 100-subject pilot study, or optional expanded single arm study (262 patients) the objective is to establish a device associated thrombus (DAT) rate at 3 months and 1 year within 1.5% or less deviation from published DAT rates at 3.9% (Saw, J., et al). Comparison will be made to published data on Watchman LAA closure utilizing the 45-day warfarin after implant followed by six-month dual antiplatelet regimen, or registry data from European experience on Watchman and Amulet/ACP LAA closure systems.

Patients can be consented for the trial on the day of implantation or up to one month prior in clinic during consultation for LAA closure. This is an unblinded, single arm prospective study. Study exit visit will be coordinated with final twelve-month follow-up imaging after LAA closure implantation.

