Kaneko et al. [ref 20] 78 patients (50 males,  $72 \pm 8$  years, average CHA2DS2-VASc score of  $4.3 + 1.8$ ) who had undergone WATCHMAN implantation. WATCHMAN was successfully implanted in all patients and four (5%) developed DRT. Patients with DRT were more often female (75 vs. 34%,  $p = 0.094$ ). CHA2DS2-VASc score was higher for patients with DRT ( $6.3 \pm 2.5$  vs.  $4.2 \pm 1.7$ ,  $p = 0.022$ ). Chronic kidney disease (100% vs. 43%,  $p = 0.024$ ) and deep implantation of the device, which was defined as implant position below the LAA ostial plane (75 vs. 24%,  $p = 0.026$ ), were more common in patients with DRT. HAS-BLED score ( $4.5 \pm 1.0$  vs.  $3.5 \pm 1.1$ ,  $p = 0.074$ ) was higher and oral anticoagulants (50 vs. 84%,  $p = 0.086$ ) were less commonly prescribed for patients with DRT. Multivariable logistic regression analysis showed that higher CHA2DS2-VASc score ( $p = 0.022$ , OR 2.8) and deep implantation ( $p = 0.032$ , OR 24.7) were associated with DRT. These results suggest the possible role of CHA2DS2-VASc scores and implantation depth in the development of DRT after percutaneous LAA closure using the WATCHMAN device.

With a single arm non-inferiority trial design to show the absolute rate of DAT is less than the control rate of 3.9% by a non-inferiority margin of 1% having a power 80% to detect a 1.4% difference at 0.05 level of significance, we would need 262 total subjects enrolled and reaching imaging endpoint evaluation. The initial study will begin with pilot to 100 subjects (with 46% power) with an option to expand if additional funding source is obtained.

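### The objective of a DAT rate within 1.5 points of 3.9% is undefined and has no supporting calculation: as an interval neither 100 nor 262 subjects can meet it, and as an observed rate it is a poor criterion

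*Combined protocol and SAP*

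**What the plan says.** The objective stands in section 3 (Inclusion and Exclusion Criteria), in the paragraph after the exclusion list that estimates how much drug is needed. It covers both sizes, "With either the 100-subject pilot study, or optional expanded single arm study (262 patients"), and says that "the objective is to establish a device associated thrombus (DAT) rate at 3 months and 1 year within 1.5% or less deviation", measured from a published benchmark: "within 1.5% or less deviation from published DAT rates at 3.9" percent. Nothing there or elsewhere says what must lie within 1.5 points (estimate, whole interval or upper limit), at what confidence, or how 1.5 was chosen.

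The Statistical Methods/Calculations section sizes the trial on other figures. It takes a "control rate of 3.9% by a non-inferiority margin of 1" percent, "having a power 80% to detect a 1.4% difference at 0.05 level of significance", and concludes that "we would need 262 total subjects enrolled and reaching imaging endpoint evaluation". It gives the 100-subject pilot 46% power on the same test. Section 2 (Study design) repeats the 3.9% control rate, the 1-point margin and the 1.4-point difference. The 1.5-point figure appears in neither of these sections.

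**The concern.** The same numerical target is attached to two sizes that differ by a factor of 2.6, and the verb used is to establish. A DAT rate near 3.9% means about 4 events in 100 subjects or 10 in 262, and counts that small leave wide uncertainty around the rate.

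The pilot is the part of the study that does not depend on further funding, and this sentence is the only numerical objective that section 3 gives it. The Statistical Methods section describes its purpose as showing a comparable DAT rate. With the criterion undefined, a pilot with 3, 4 or 5 events could be described as having met its objective, although its data would be compatible with rates well outside the band.

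**Working it through.** **Inputs.** Benchmark 3.9%, deviation 1.5 points, sizes 100 and 262 (section 3). Margin 1 point, difference 1.4 points, power 80%, level 0.05, pilot power 46% (Statistical Methods/Calculations). Every subject is assumed to be imaged. The 95% and 90% levels used for intervals are assumptions, because the plan names none for this objective.

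**1. The plan's own sizing reproduces.** Limit 3.9% + 1% = 4.9%; assumed true rate 3.9% − 1.4% = 2.5%; one-sided 0.05 (sidedness is not stated, but this choice reproduces the figure); variance at 2.5%.
- n = (1.645 + 0.842)² × 0.025 × 0.975 / 0.024² = 261.6, so 262.
- Power at 100: 0.024 / √(0.025 × 0.975 / 100) − 1.645 = 1.537 − 1.645 = −0.108, which gives 45.7% against the stated 46%.

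**2. The band.** 3.9% ± 1.5 points is 2.4% to 5.4%. An observed rate inside it means 3 to 5 events of 100, or 7 to 14 of 262 (0.024 × 262 = 6.3; 0.054 × 262 = 14.1).

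**3. Reading A: the whole interval must lie inside the band.** Exact (Clopper-Pearson) intervals need a lower limit of at least 2.4% and an upper limit of at most 5.4%.

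| Size | Level | Events needed for lower limit | Events allowed by upper limit |
|---|---|---|---|
| 100 | 95% | at least 7 | 0 |
| 100 | 90% | at least 6 | at most 1 |
| 262 | 95% | at least 13 | at most 6 |
| 262 | 90% | at least 12 | at most 7 |

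The two conditions never overlap, so no result can satisfy this reading. For scale, the Wald 95% half-width at 3.9% is 1.96 × √(0.039 × 0.961 / n): 3.8 points at 100 and 2.3 at 262. At 90% it is 3.2 and 2.0.

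**4. Reading B: the observed rate must lie inside the band.** Binomial probabilities:

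| True rate | 3 to 5 of 100 | 7 to 14 of 262 |
|---|---|---|
| 2.5% (the plan's assumed rate) | 42% | 48% |
| 3.9% | 56% | 80% |
| 6.0% | 38% | 38% |

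The 6.0% rate is an illustration above the plan's 4.9% limit. At 2.5% most of the misses fall on the favourable side: the observed rate is below 2.4% in 54% of trials of 100 and 52% of trials of 262.

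**5. Reading C: only the upper limit must be below 5.4%.** With the exact two-sided 95% interval this needs 0 events of 100 (8% chance at a true 2.5%) or at most 6 of 262 (52% at 2.5%, 11% at 3.9%). With a one-sided 95% limit it needs at most 1 of 100 (28% at 2.5%) or at most 7 of 262 (67% at 2.5%).

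**6. What each size can report.** Exact 95% intervals: 3/100 gives 0.6% to 8.5%; 4/100 gives 1.1% to 9.9%; 5/100 gives 1.6% to 11.3%; 10/262 gives 1.8% to 6.9%.

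**The case against.** The strongest reply is that the sentence states an aim, a maximum distance from a published benchmark, and does not promise an estimation precision. It mentions no interval, half-width or confidence level and sits in a paragraph about drug supply. The statistical criterion is elsewhere, and the plan openly calls the 100-subject stage a pilot with 46% power.

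Much of this stands. A reader might infer that the plan promises a 95% half-width of 1.5 points and has got its arithmetic wrong. The documents do not support that: they claim no half-width, they show no calculation behind 1.5 that could be wrong, and the calculation they do show reproduces. Nor is the objective unattainable on every reading. The observed-rate reading can be met at either size, and the upper-limit reading can be met with limited probability, mainly at 262.

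A reader might also infer that an unsafe regimen could pass. The plan does not define any DAT rate as unsafe, and its background section says the link from DAT to ischemic stroke has been hard to determine. What can be said is that 6.0% exceeds the plan's own non-inferiority limit. Likewise, an upper bound of nearly 10% belongs to 4/100 only; 3/100 stops at 8.5%.

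The reply does not settle what the sentence means or why one target fits both sizes. The 46% power belongs to the 1-point margin test and says nothing about the 1.5-point objective.

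**Conclusion.** The concern holds as a defect of definition and support. The 1.5-point objective has no stated estimand, confidence level or calculation, and it differs from the quantity on which the trial is sized. If the whole interval must lie in the band, neither size can meet it at 95% or 90%. If the observed rate must lie in the band, the objective separates rates poorly: it is met 56% (100) or 80% (262) of the time at a true 3.9%, and 38% at either size at a true 6.0%. If only the upper limit counts, the pilot has at most a 28% chance even at the plan's assumed 2.5%.

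These figures assume complete imaging, exact binomial intervals and the confidence levels named. Missing imaging would widen the intervals. The conclusion does not extend to the 262 or 46% figures, and it does not imply that the trial needs more subjects.

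**What to change.** In the section 3 paragraph on drug required:
- Remove the statement that either size establishes the DAT rate within 1.5 points of 3.9%.
- State that the 3-month and 1-year DAT rates will each be reported with an exact 95% interval, and print the expected precision, for example 1.1% to 9.9% for 4/100 and 1.8% to 6.9% for 10/262, wider if imaging is missing.
- State that the pilot estimates the rate and does not by itself support a conclusion of comparability, and that any such conclusion rests on the non-inferiority criterion in section 2 and in Statistical Methods/Calculations.

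This changes protocol wording only; enrolment stays as planned. The cost is that the stated precision becomes less favourable.

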Event rates for bleeding after Watchman versus warfarin show superiority after 6 months when clopidogrel is discontinued. This is where the net clinical benefit of LAAC is seen, leading to improved long term outcomes and ultimately the rationale for FDA approval of the Watchman device. The role of dual anti-platelet therapy, or the use of 325mg ASA versus 81 mg ASA long term is not supported by any specific literature, and was carried over from previous trials with use of coronary stents, and PFO and ASD occluder devices. Once the LAA device has complete occlusion with no flow into the LAA and surface endothelialization, it is plausible that ASA 81mg is a sufficient recommendation long term. This has recently been established in European AF guidelines on LAA closure for patients contra-indicated to OAC, supporting single or dual anti-platelet therapy after implant.

However, this potentially sets up an increased risk of device associated thrombus (DAT). If an alternative post procedure regimen using 90 days of dabigatran plus 81mg ASA alone is employed, eliminating the use of clopidogrel, we may reduce both major bleeding events, and reduce device associated thrombus rates at 1 year follow up. It would not be expected to impact ischemic stroke rate, but this could be implied if fewer DAT are observed.

In conclusion, LAA closure is becoming a reasonable strategy for patients at high risk for stroke (CHADS 2 Vasc score 3-9) and high risk for bleeding on long term OAC (HAS BLED score 2-6). The FDA labeled strategy for medical management after Watchman implant is loosely supported scientifically, and still exposes patients to increased bleed risk up to 6 months after implant due to the use of DAPT. A shorter and simplified use of dabigatran BID for 90 days post LAAC with ASA 81mg, followed by ASA 81mg daily long term may reduce bleeding events, and have a beneficial impact on lowering the rate of DAT. Praxbind is a specific monoclonal anti-body available for dabigatran reversal. All study centers will have Praxbind available for use in the event of a major bleed, (i.e., subdural or intracranial bleed, or major bleed requiring transfusion), or in case of unexpected or emergent surgery.

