## **2. Study design:**

Single arm, prospective unblinded study on post Watchman LAA closure device implant anti-coagulation management at a primary center (Vanderbilt Medical Center) and up to 5 additional high volume LAA implant centers. This trial will be designed to evaluate the use of dabigatran for 90 days post implantation of an LAA closure device (Watchman LAA Closure Device, Boston Scientific Inc.). The drug will be initiated on the morning following device implantation, taken BID per package insert dosing and until follow-up 90-day post implant TEE. Aspirin monotherapy will be utilized in conjunction at 81 mg for up to 12 months, after which the patients will be exited from the study and further treatment decisions will be made by the following physician (see Schedule of Study Procedures at end of protocol). The objective of this trial is to evaluate safety and efficacy of a 90-day period of dabigatran etexilate following LAA closure to prevent device associated thrombus, while minimizing adverse bleeding by eliminating the need for clopidogrel. This is a single arm pilot study with the option (pending collaboration with additional funding source) to expand to a full single arm non-inferiority trial design with 80% power to detect a 1.4% difference with the non-inferiority margin 1% in absolute rate of DAT (control rate 3.9%).

Prospective, non-randomized single arm study. Comparison will be made to historical controls based on published one year DAT rates from PROTECT-AF, PREVAIL clinical trials, and EWOLUTION, and ACP/Amulet registries.

Echocardiography (TEE) will be performed at 90 days (3 months, +/- 2-week window), and again at 1-year post implant (+/- 4 weeks). Selected images will be interpreted by echo lab at coordinating center in an anonymous fashion (patient data de-identified). Ideal imaging will incorporate 0, 45, 90 and 135 degree angled views on the device at follow up.

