### **Statistical Methods/Calculations:**

Statistical sample size calculation to establish comparable DAT rate with the prescribed regimen:

Available data for background on DAT;

Overall incidence of DAT was 3.9% (82 DAT for 2118 implanted devices)

Lempereur et al. Meta-Analysis [ref 19]: 30 studies describing DAT events were included in the analysis. The overall incidence of DAT was 3.9% (82 DAT for 2118 implanted devices). The median time from procedure to diagnosis of DAT was 1.5 months (IQR: 0-2.9). Most cases were diagnosed with transesophageal echocardiogram (TEE). The treatment consisted of low molecular weight heparin (LMWH) in 45.5% of cases, and oral anticoagulation (OAC) or other treatment modalities in 54.5%. Complete thrombus resolution was achieved in 95.0% of cases (100% with LMWH and 89.5% with OAC). Treatment duration varied greatly with a median treatment duration of 45 days (IQR: 14-

135). Clinical events related to DAT consisted of neurologic events namely two transient ischemic attacks (2.4%) and four ischemic strokes (4.9%).

Saw et al [ref 7]. 339 analyzable TEE in follow up. Patients' mean age was  $74.4 \pm 7.5$  years, and 67.3% were men. The mean CHADS2 score was  $2.7 \pm 1.3$ , the mean CHA2DS2-VASc score was  $4.3 \pm 1.5$ , and the mean HAS-BLED score was  $3.0 \pm 1.2$ . Peri-procedural major adverse events occurred in 2.4%. Median clinical follow-up duration was 355 days (range 179 to 622 days). Follow-up transesophageal echocardiography was performed after a median of 134 days (range 88 to 227 days). Device-associated thrombus was observed in 3.2% Independent predictors of device-associated thrombus were smoking (odds ratio: 5.79;  $p = 0.017$ ) and female sex (odds ratio: 4.22;  $p = 0.027$ ).

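### The stated DAT objective (within 1.5 points of 3.9%, no direction given) conflicts with the plan's own one-directional non-inferiority design (margin 1 point, implied bound 4.9%).

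*Combined protocol and SAP*

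**What the plan says.** Two statements describe what the study should show about DAT.

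- **Section 3, the paragraph on drug required for the study (after the exclusion list).** "With either the 100-subject pilot study, or optional expanded single arm study (262 patients) the objective is to establish" a "DAT) rate at 3 months and 1 year within 1.5% or less deviation from published DAT rates at 3.9% (Saw, J., et al". No direction is attached to the deviation, and two time points are named.
- **Section 2, Study design.** The optional expansion is a single-arm non-inferiority trial with "80% power to detect a 1.4% difference with the non-inferiority margin 1% in absolute rate of DAT (control rate 3.9" percent). Statistical Methods/Calculations repeats this: the aim is to "show the absolute rate of DAT is less than the control rate of 3.9% by a non-inferiority margin of 1" percent, at a 0.05 level, with 262 subjects reaching imaging and 46% power for the pilot of 100.

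The expected direction is downward. The Background says of the regimen that "we may reduce both major bleeding events, and reduce device associated thrombus rates at 1 year follow up". The primary endpoint is DAT at 1-year imaging.

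On the source of 3.9%, Statistical Methods reports from the meta-analysis (ref 19): "The overall incidence of DAT was 3.9% (82 DAT for 2118 implanted devices"). For the ACP registry (ref 7) it reports: "Device-associated thrombus was observed in 3.2" percent. No section reconciles the 1.5% deviation with the 1% margin.

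**The concern.** DAT is a harm, so a lower rate is better. A target defined as closeness to 3.9% in either direction treats a rate near zero as a miss. Its upper end also lies above the bound implied by the non-inferiority margin. The study is unblinded, has one arm and is compared with published rates. With two numerical statements that rarely agree, the choice of which one counts could be made after the results are known.

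**Working it through.** **Inputs.** Control rate 3.9% (82/2118 = 3.87%), margin 1 point, difference 1.4 points, power 80%, level 0.05, N = 262, and pilot N = 100 with 46% power (Study design; Statistical Methods). Allowed deviation 1.5 points (section 3).

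**1. Reproduce the plan's figures.** Take the bound as 3.9% + 1% = 4.9% and the true rate as 3.9% − 1.4% = 2.5%, with one-sided 0.05 and the variance at the true rate:

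n = (1.645 + 0.842)² × 0.025 × 0.975 / (0.049 − 0.025)² = 261.6, so 262.

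Power at n = 100: Φ(0.024 / √(0.025 × 0.975 / 100) − 1.645) = 45.7%, stated as 46%.

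Both figures reproduce. The 4.9% is not printed in the protocol. Of the combinations tried, this is the only one that returns 262; two-sided 0.05, for example, gives 332. With a 1.5-point margin (bound 5.4%) the same formula gives 179.2, so 180 subjects, with 91% power at 262 and 58% at 100. The two figures are not interchangeable.

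**2. The literal band.** 3.9 ± 1.5 = 2.4% to 5.4%. This corresponds to 3-5 DAT of 100, or 7-14 of 262.

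- Too low: 0-2 of 100, or 0-6 of 262.
- In the band but above 4.9%: 5 of 100 (5.0%), and 13 or 14 of 262 (4.96%, 5.34%).

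Exact binomial probabilities if the band were used as the criterion:

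| True rate | n = 100: in band | n = 100: below | n = 262: in band | n = 262: below |
|---|---|---|---|---|
| 1% | 8% | 92% | 2% | 98% |
| 2.5% (design assumption) | 42% | 54% | 48% | 52% |
| 4.9% (implied bound) | 51% | 13% | 67% | 3% |

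A regimen at the bound would meet the band more often than the regimen the design hopes for.

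**3. The non-inferiority criterion.** Largest counts whose one-sided 95% upper limit is below 4.9%:

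| Method | n = 100 | n = 262 |
|---|---|---|
| Exact | 1 (limit 4.66%; 2 gives 6.16%) | 6 (limit 4.47%; 7 gives 4.96%) |
| Wald | 2 (limit 4.30%; 3 gives 5.81%) | 8 (limit 4.80%; 9 gives 5.29%) |

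With exact limits, no result meets both this and the band at either size. With Wald limits, only 7 or 8 of 262 does.

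**4. If 1.5 points meant precision.** The 95% half-width at 3.9% is 1.96 × √(0.039 × 0.961 / n): 3.8 points at n = 100 and 2.3 points at n = 262. Neither size delivers 1.5.

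**The case against.** The strongest reply is that the sentence was never meant as a pass/fail rule. It stands in a paragraph about drug supply, the formal design is elsewhere, and no section says the trial will be judged by the band. Since the protocol aims to prevent DAT, a meaning of no more than 1.5 points worse is plausible. This stands: on that reading the direction problem disappears, and the probabilities in the table describe a rule the sponsor may not have intended. The mismatch of 1.5 with 1 remains.

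A reader might infer that the band is the pilot's only stated goal. It is not. The Study design section gives a general safety and efficacy aim of preventing DAT, and Statistical Methods gives the pilot a power for the non-inferiority comparison. The band is the only numerical DAT target expressly applied to both sizes.

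The 5.4% and 4.9% are also different kinds of limit. The first reads as a limit on an observed rate; the second bounds the true rate. This is a fair caution, but it widens the practical gap, as step 3 shows. The Statistical Methods wording could even be read as requiring a rate 1 point below control (2.9%); 5.4% is looser than that too.

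Finally, a reader might infer that 3.9% was taken from the wrong study. Section 3 gives an author name without a reference number. That author leads the ACP registry paper (3.2%) but is also listed on the meta-analysis (3.9%), and Statistical Methods attributes the figure correctly. This is a clerical slip.

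**Conclusion.** The concern holds as an inconsistency between two stated targets. On the literal text, the section 3 objective and the non-inferiority design agree on almost no result: none with exact limits, and only 7 or 8 of 262 with Wald limits. The literal reading takes the deviation as two-sided and applied to the observed rate. The 4.9% is derived, and supported by reproducing both 262 and 46%. Under a one-sided reading the 1.5 versus 1 conflict remains; under a precision reading neither sample size is adequate.

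Two stronger conclusions are not supported. The documents do not show that a very low DAT rate would actually be declared a failure, because no section makes the band a formal test. Nor is the sample size in error on this point: 262 and 46% follow from the plan's own inputs.

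**What to change.** Replace the section 3 sentence with one directional objective tied to the 1-year primary endpoint and the existing margin: to show that the one-sided 95% upper confidence limit of the 1-year DAT rate is below 4.9% (3.9% + 1%), with the interval method named. Report the 3-month rate, and the pilot rate if the study is not expanded, descriptively with a confidence interval. Delete the 1.5% figure. Cite ref 19 for 3.9%.

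The objective must rest on the confidence limit. A rule that the observed rate be at most 4.9% would pass 48% of the time at a true rate of 4.9% with n = 262 (45% with n = 100), and would still disagree with the non-inferiority test for 9-12 of 262.

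Cost: one sentence in an amendment, with no change to visits or procedures. N = 262 and the 46% pilot power stay as computed under the plan's normal approximation. The choice of interval has consequences that should be seen when it is named. At n = 262 and a true 2.5%, the Wald rule passes 79% of the time but also passes 10% of the time at a true 4.9%; the exact rule passes 52% and 2.6%. The downside is that observed rates above about 2.3% (exact) or 3.1% (Wald) at n = 262 no longer meet the objective.
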